Study aim:	Examination of prevalence, incidence and risk factors of community acquired pneumonia (CAP) and its interaction with comorbid diseases in a representative sample of outpatients and inpatients
Patients:	Male and female patients ≥ 18 years of age
Study design:	Prospective and observational study
Main objectives:	
• Estimation of prevalence/incidence of CAP• Examination of the reciprocal relation between CAP and comorbidity• Evaluation of CAP in immunosuppressed patients• Determinants of CAP in HIV patients• Establishment of a database on antimicrobial resistance• Information concerning pathogens and pathogen/host interaction• Establishment of a genetic database concerning pathogens and strains of CAP patients
Study arms:	
1) Outpatients or inpatients with CAP, without HIV infection2) Outpatients or inpatients with CAP, with HIV infection3) Outpatients or inpatients with CAP, with Immunosuppression
Interventions:	None prescribed or planned
Inclusion criteria:	
• Age ≥ 18• Radiological proof of pulmonary infiltrate (primarily chest x-ray or CT)• Signed informed consent
Further inclusion criteria (at least one should be fulfilled):	
• Presence of cough• Presence of purulent sputum• Pathologic lung auscultation (crackles)• Fever
Exclusion criteria:	
• Hospitalization longer than 48 hours prior to diagnosis of current pneumonia• Non-infectious infiltrate• Newly diagnosed, active pulmonary tuberculosis within the last 2 months
Study duration:	Unlimited, depending on funding possibilities (study duration according to funding duration)
Examination time points:	Inpatients only: Visit 1/baseline, visit 2 after 3-5 days, visit 3 after 7-10 days, telephone interviews after 4 weeks and after 6 months from inclusion date

Outpatients only:

Visit 1/baseline, telephone interviews after 4 weeks and after 6 months from inclusion date

Examinations:

Inpatients only:

- Baseline: anamnesis (incl. pneumonia-specific medication and co-mediation of chronic underlying diseases and comorbidities), physical examination, laboratory tests, chest x-ray, hospitalization within the last 3 months, for HIV patients with community acquired pneumonia an additional data entry form, for immunosuppressed patients an additional data entry form
- Visits after 3-5 and 7-10 days: patient's status assessment and medications, clinical stability criteria, complications, laboratory tests
- Visits after 28 days (by telephone): patient's status assessment and medications, complications, hospitalization
- Visits after 180 days (by telephone): survival status

Outpatients only:

- Baseline: anamnesis (incl. pneumonia-specific medication and co-mediation of chronic underlying diseases and comorbidities), physical examination, laboratory tests, chest x-ray, for HIV patients with community acquired pneumonia an additional data entry form, for immunosuppressed patients an additional data entry form
- Visits after 28 days (by telephone): patient's status assessment and medications, complications, hospitalization
- Visits after 180 days (by telephone): survival status

Number of patients: Approx. 500 per year

Number of study centers: Approx. 20-30

5 Summary

The aim of this study is to determine prevalence, incidence and risks for CAP outpatients and inpatients through

1. Establishment of a database on antimicrobial resistance, pathogens and pathogen/host interaction, chronic underlying diseases, course of the disease and risk identification
2. Establishment of a genetic database
3. CAP in immunosuppression as a sub-study
4. CAP in HIV as a sub-study
5. Investigation into the reciprocal relationship between CAP and comorbidity

Approx. 500 patients at the age of ≥ 18 years shall be included in a cohort-study through prospective observation. The medical histories and the medication anamnesis will be recorded by the beginning of the study, especially concerning the pneumological events and predefined comorbid diseases. Diagnosis is proven by detection of an infiltrate using imaging. Relevant vital parameters are measured and the acute course of the disease documented in detail. Additionally, biomaterials from the upper and lower respiratory tracts as well as blood and urine samples are taken.

Timely visits are carried out for all inpatients at the point in time of day 3-5 and day 7-10. During these visits, the status of the patients, the therapies concerning the current disease and the comorbid diseases are documented. Clinical stability criteria and complications are recorded. Chest x-ray or CT, if performed within the clinical routine, will be documented. Repeated blood samples are collected.

Further telephone interviews are carried out 28 and 180 days after inclusion. During every telephone interview, the specific medical history concerning the previous time period will be documented.

Furthermore, for patients in the HIV sub-study, specific HIV questions will be raised during the Baseline and the visits after 28 and 180 days.

For patients with immunosuppression specific questions will be raised during the Baseline and the visit after 28 days.

The study will be carried out according to the recommendations of “Good Epidemiological Practice” (GEP) by the “German Association of Epidemiology” (DAE) and the appropriate regulations of Good Clinical Practice (GCP) and the Helsinki Declaration.

6 Objectives

The objective of this study is the investigation of the prevalence, incidence and risk factors of community acquired pneumonia (CAP) and their interaction with comorbid diseases in an unselected group of adult patients under the care of GPs, specialists and inpatient treatment.

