6.5.2 Central CAPNETZ Biobank

The services of the Central CAPNETZ biobank at the Hannover Medical School can be summarized as follows:

CAPNETZ STIFTUNG Geschäftsstelle • Medizinische Hochschule Hannover
[name] • [contact] • [contact]
[contact] • www.capnetz.de

Administration, quality management, sample shipping, processing and storage for scientific purposes of the CAPNETZ FOUNDATION.

Address:

Hannover Unified Biobank (HUB)
Medizinische Hochschule Hannover
CRC Hannover
[name]
[name]

The Management system of the biobank is certified by TÜV NORD according to DIN EN ISO 9001:2008.

7 Study Design

Currently there are approx. 13,000 patients in the prospective-observational study, the CAPNETZ study. The patients are individually followed-up (successively from the reference date 01.07.2002) for a time period of six months. The patients are identified in the outpatient or inpatient departments of the hospitals or practices and are recruited by their treating physicians (mainly specialists). All of the patients who fulfill the inclusion and exclusion criteria and who are verified as having newly acquired non-nosocomial pneumonia are invited to participate. No interventions are planned for this study; the physicians treat their patients as they usually do.

8 Patients

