8.1 Sample size

It is planned that within the study duration from 01.01. 2020 approx. 500 patients will be included each year in order to obtain representative data for prevalence and incidence estimation.

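### The protocol claims an unselected, representative cohort and gives this as the reason for 500 patients a year, but its recruitment design cannot deliver that property

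*Protocol*

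**What the plan says.** Three places in the protocol make a population claim.

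- Synopsis, study aim: CAP is examined "in a representative sample of outpatients and inpatients".
- Section 6 (Objectives): the investigation is "in an unselected group of adult patients under the care of GPs, specialists and inpatient treatment".
- Section 8.1 (Sample size): about 500 patients a year are planned "in order to obtain representative data for prevalence and incidence estimation".

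The recruitment text describes something narrower.

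- Section 7 says that patients "are recruited by their treating physicians (mainly specialists"), and that all who meet the criteria and have verified non-nosocomial pneumonia are invited.
- Section 6.5.1 describes centres led by experts in respiratory medicine whom CAPNETZ names. Patients may be inpatients, clinic outpatients or outpatients of practice networks.
- Section 8.2 requires signed consent and radiological proof of an infiltrate.
- Section 9 sets a limit of 48 hours from presentation to inclusion and admits patients from either setting, with no proportion fixed.
- Section 15.3 has samples and data destroyed when an incapacitated patient dies and consent was not obtained.

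The size is stated in two ways. The synopsis gives "Approx. 500 per year" and Section 8.1 agrees, while Section 5 says "Approx. 500 patients at the age of ≥ 18 years shall be included in a cohort-study through prospective observation".

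**The concern.** A reader of the synopsis would take a proportion or risk from this cohort as an estimate for adults with CAP in general. That requires either a sampling scheme that gives each setting its proper weight or a way to correct the weights afterwards. The protocol states no sampling frame, setting quota or weighting. The ratio of inpatients to outpatients follows from where and how centres recruit, so it is not an estimate of the ratio in the disease. Section 8.1 adds an error of reasoning: it offers a number of patients as the means of becoming representative.

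One loss is tied to outcome. Destroying the data of patients who die before consent is obtained may be ethically necessary, but it removes severe cases and would bias mortality downward by an unknown amount.

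The protocol's background (Section 6.3) says that results from the cohort influence the national guideline for CAP, so the population to which a figure applies matters in practice.

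**Working it through.** **The plan's own figure.** The 500 per year comes with no precision target or other input, so there is no calculation to reproduce.

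**Step 1: what 500 patients provide.** Input: the 6-8% mortality in Section 6.3. The 95% half-width is 1.96 × √(p(1−p)/n).

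- p = 0.06, n = 500: 1.96 × √(0.06 × 0.94/500) = 2.1 points.
- p = 0.08, n = 500: 1.96 × √(0.08 × 0.92/500) = 2.4 points.

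This is random error only. It shrinks with n whoever is enrolled, and says nothing about whether the right patients are in the sample.

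**Step 2: what the unfixed mix can do.** Pooled risk = w × p_in + (1−w) × p_out, where w is the inpatient share. Inputs:

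- p_in = 6% or 8%. Section 6.3 calls this overall mortality, in a paragraph about hospital admissions. Reading it as the inpatient risk is an assumption.
- p_out = 1%. The protocol gives no outpatient figure, so this is assumed; a range of 0.5-2% is also shown.
- w = 30% to 90%. This is assumed, because the protocol fixes no share.

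| p_in | p_out | w = 30% | w = 50% | w = 70% | w = 90% | Shift, 30% to 90% |
|---|---|---|---|---|---|---|
| 6% | 1% | 2.5% | 3.5% | 4.5% | 5.5% | 3.0 points |
| 8% | 1% | 3.1% | 4.5% | 5.9% | 7.3% | 4.2 points |

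The shift equals 0.6 × (p_in − p_out). Over the assumed outpatient range it runs from 0.6 × (6 − 2) = 2.4 points to 0.6 × (8 − 0.5) = 4.5 points.

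**Step 3: compare.** With 1% for outpatients, the shift is 3.0 points against a half-width of 2.1 (inpatient risk 6%), and 4.2 against 2.4 (inpatient risk 8%). Even with 2% for outpatients it is 2.4 against 2.1 and 0.6 × (8 − 2) = 3.6 against 2.4. Over this range of mixes, a change in who is enrolled can move the pooled figure by more than its stated uncertainty, with no change in the disease.

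**Step 4: the two statements of size.** At 7% mortality the half-width is 2.2 points for 500 patients in all. For 2,500, which is five years at 500 per year (the five years are an assumption, since duration is open), it is 1.0 point. The two readings describe studies of different precision.

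**The case against.** The strongest defence is the rule in Section 7 that every eligible patient is invited. Section 16.1 supports it: centre contracts oblige centres to inform all potential patients. On paper this is consecutive invitation, and it is a fair basis for saying that physicians are not meant to pick patients. This stands. It does not remove selection by centre, specialty, consent, the time window or death before consent. Adherence also cannot be checked, because the protocol describes no count of eligible, invited and refusing patients.

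The GP wording is also less contradictory than it looks. Mainly specialists does not mean only specialists, and Section 6.5.1 admits practice networks. What remains is that nothing secures a GP share.

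Three stronger readings may tempt a reader, and the documents do not support them.

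- *The low rate proves selection.* With 20-30 centres, 500 a year is 25 to 16.7 patients per centre-year, or 2.1 to 1.4 a month. Without the number of eligible patients per centre, which the protocol does not give, this shows nothing.
- *Pooled results describe no population.* They describe consenting CAP patients at participating centres in the mix enrolled. Comparisons within the cohort, the biobank and the resistance database do not need a representative sample.
- *Pooling is planned and must be banned.* Section 14 defines no pooled estimate. Setting is known for each patient, since visit schedules differ by setting, and stratified tables may sit in an analysis plan that is not shown.

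**Conclusion.** The concern holds as a correction to what the protocol claims; it is not a finding that the cohort is unusable. The words unselected and representative, and the rationale in Section 8.1, state a property that the described recruitment does not provide. Sample size cannot supply it.

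The 3.0-4.2 point shift illustrates how far an unfixed mix could move a pooled mortality; it is not an estimate of actual bias. It rests on reading the 6-8% as inpatient risk, on an assumed outpatient risk of 1%, and on inpatient shares between 30% and 90%. The sign and the mechanism need only that risk differs by setting. The size of the loss from death before consent cannot be derived from the protocol.

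The conflict between Section 5 and the synopsis with Section 8.1 is a plain slip, separate from representativeness. Two places agree on a yearly figure and only the summary drops it.

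**What to change.** 1. In the synopsis and Section 6, replace the representative and unselected wording with *consenting CAP patients recruited at participating CAPNETZ centres*. In Section 8.1, delete representativeness as the reason for the number.
2. In Section 14, add a sentence that prognosis, pathogen and resistance results are shown separately for inpatients and outpatients, and that any pooled figure is accompanied by the in-/outpatient mix behind it.
3. In Section 5, change the total to *approx. 500 per year*.
4. As a secondary suggestion, have each centre keep an anonymous aggregate count of eligible, invited and enrolled patients by setting. It should hold totals only, so that it respects the rule in Section 16.1 against recording a patient's data before signed consent. Enrolment is open-ended, and counts not kept now are unlikely to be recoverable later.

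The cost is a more modest claim, wider intervals within each setting and a small tally burden. Section 9 already has centres test eligibility. Under Section 16.4 a modified study plan also goes back to the ethics committees, so the changes are best made in one amendment.

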6.1 Primary Objectives

The main objectives are:

1. Estimation of prevalence/incidence of CAP
2. Improvement of diagnostic accuracy through integration of clinical and microbiological data
3. Documentation of comorbid diseases and analysis of their role as a risk factor
4. Investigation of the influence of CAP on the course of chronic underlying diseases
5. Investigation of HIV as a risk factor
6. Evaluation of importance, risk factors, spectrum of pathogens and course of community acquired pneumonia in patients with pre-existing congenital, acquired or therapy-associated immunosuppression
7. Establishment of a central sample and strain biobank
8. Establishment of a central database concerning antimicrobial resistance
9. Information about pathogens and pathogen/host interaction
10. Establishment of a genetic database concerning pathogens and strains

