8.2 Inclusion Criteria

The following inclusion criteria must be fulfilled:

- Age ≥ 18
- Radiological proof of pulmonary infiltrate (primarily by chest x-ray or CT)
- Signed informed consent

Further inclusion criteria (at least one must be fulfilled):

- Presence of cough
- Presence of purulent sputum
- Pathological lung auscultation (crackles)

- Temperature $\geq 38,3^{\circ}\text{C}$ (rectal) or $\geq 37,8^{\circ}\text{C}$ (axillary/oral/auricular/sublingual)

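### The stated aim includes risk factors of CAP and its determinants in HIV patients, but only CAP cases are enrolled, so the study's own data cannot estimate the risk of acquiring CAP

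*Protocol*

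**What the plan says.** The synopsis gives the study aim as "Examination of prevalence, incidence and risk factors of community acquired pneumonia (CAP"), and its main objectives include "Determinants of CAP in HIV patients". The lead sentence of Section 6 repeats the aim: "investigation of the prevalence, incidence and risk factors of community acquired pneumonia (CAP").

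Among the primary objectives in Section 6.1, number 3 is "Documentation of comorbid diseases and analysis of their role as a risk factor" and number 5 is "Investigation of HIV as a risk factor". Neither says what the exposure is a risk factor for.

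On enrolment, the first study arm in the synopsis is "Outpatients or inpatients with CAP, without HIV infection". The other two arms are CAP patients with HIV and CAP patients with immunosuppression. Section 8.2 requires "Radiological proof of pulmonary infiltrate (primarily by chest x-ray or CT"), and Section 7 invites only patients with verified, newly acquired, non-nosocomial pneumonia. Follow-up covers health status, medication, hospitalization and complications at 28 days and survival at 180 days. Inpatients have two additional visits, at days 3-5 and 7-10.

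**The concern.** A risk factor for, or determinant of, acquiring CAP is identified by comparing people who get CAP with people who do not, or by comparing exposure among cases with exposure in the population that produced them. This cohort supplies only cases. The outcome does not vary, and the Protocol names no source for the other side of the comparison.

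At stake is what the study can conclude. Comparing CAP patients with and without HIV answers a question about course, death or pathogens given CAP. That is a useful question, but it differs from whether HIV makes CAP more likely. Section 6.4.2 lets outside researchers apply for the data within the foundation's objectives, so the objectives should say which of the two questions the data can support.

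**Working it through.** The Protocol gives no figure to reproduce here. The 500 patients per year in Section 8.1 come without a precision target, power or effect size. The check is therefore one of identifiability.

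**Step 1: which outcome is meant.**
- Synopsis aim and Section 6 lead sentence: risk factors of CAP itself.
- Synopsis HIV line: determinants of CAP among HIV patients.
- Section 6.1, objectives 3 and 5: no outcome named.
- Section 6.2, secondary objective 5: risk factors for unusual pathogens or a severe course, in immunosuppressed patients. Here the Protocol does name a within-CAP outcome.

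**Step 2: who is observed.** All three arms are CAP patients, and an infiltrate is mandatory. No HIV-positive or comorbid people without CAP are enrolled, and no catchment denominator or external reference is named. Follow-up does not create a CAP-free cohort, because everyone enters with CAP and new CAP episodes are not a listed follow-up outcome.

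**Step 3: what that identifies.** Let p1 be the HIV share among cases and p0 the HIV share in the source population. Then

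OR = [p1/(1 − p1)] / [p0/(1 − p0)].

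The study can estimate p1 but not p0. For illustration take p1 = 2%, which is assumed, so that the case odds are 0.02/0.98 = 0.02041. The values of p0 are also assumed.

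| p0 | source odds | OR |
|---|---|---|
| 0.1% | 0.001001 | 20.39 |
| 0.5% | 0.005025 | 4.06 |
| 1% | 0.010101 | 2.02 |
| 2% | 0.020408 | 1.00 |
| 5% | 0.052632 | 0.39 |

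The same study data fit strong harm, no effect or apparent protection. More patients sharpen p1 but leave p0 unknown, so the range does not narrow.

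**Step 4: what can be estimated, and how precisely.** A within-CAP comparison, such as death with versus without HIV, is identified. Take 7% mortality without HIV (the midpoint of the 6-8% in Section 6.3), an assumed 14% with HIV, two-sided α = 0.05, and

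power ≈ Φ[(|d| − 1.96·s0)/s1],

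where d is the difference in mortality, s0 the pooled standard error and s1 the unpooled standard error.

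- One year, 500 cases, assumed HIV share 2%, so 10 versus 490 patients: s0 = 0.0823, s1 = 0.1103, power = Φ[(0.07 − 0.1612)/0.1103] ≈ 20%.
- One year with an HIV share of 1% (5 patients) or 5% (25 patients): about 16% or 31%.
- Five years pooled at 2%, so 50 versus 2,450 patients: s0 = 0.0368, s1 = 0.0493, power ≈ 48%.

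The normal approximation is rough at these counts. Ten HIV patients at 14% means 1.4 expected deaths. The direction is clear: one year will not support an HIV comparison, still less an adjusted one.

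**The case against.** The best defence is that the Protocol is largely about course and prognosis, and that objectives 3 and 5 should be read that way.

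- Section 5 speaks of risks for CAP outpatients and inpatients, which can be read as risks faced by people who already have CAP.
- The research questions in Section 6.3 concern pathogens, resistance, severity markers, guidelines and vaccination. None asks which exposures lead to CAP.
- HIV-specific questions are repeated at days 28 and 180, which suits outcome research.

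This stands as far as objectives 3 and 5 are concerned: they are ambiguous, and one reading is answerable. It does not remove the synopsis aim, the Section 6 lead sentence or the HIV synopsis line, which name CAP itself.

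It can also be said that an external reference population could supply the missing comparator. In principle it could, but the Protocol names none.

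A reader might infer three stronger points that the Protocol does not support.

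- **Objectives 3 and 5 cannot be answered at all.** They can if the outcome is prognosis or pathogen, and documenting comorbid disease is achievable on either reading.
- **Objective 2, "Improvement of diagnostic accuracy through integration of clinical and microbiological data", fails because specificity for CAP cannot be estimated.** The objective does not claim specificity for CAP, and its wording points at least as well to identifying the pathogen.
- **The plan allows description only.** Section 14 says that further biometric analyses can follow, through the project route in Section 6.4.2.

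**Conclusion.** The concern holds for the aim as worded in the synopsis and in the Section 6 lead sentence, and for the HIV line in the synopsis. With cases only and no named comparator, denominator or external exposure prevalence, the study's own data cannot estimate whether HIV or comorbidity raises the risk of acquiring CAP. Objectives 3 and 5 inherit the problem if read with those statements and escape it if read as within-CAP questions, so their outcome has to be named.

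This is a gap in identification and not in precision. The odds ratios of 0.39 to 20.4 rest entirely on assumed prevalences and measure nothing about this cohort. The conclusion does not depend on those values, only on the source prevalence being unmeasured. It concerns acquiring CAP and does not extend to prognosis within CAP. No analysis plan could cure it from the study's data alone, because enrolment is fixed in the Protocol.

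**What to change.** Reword the study aim (synopsis and Section 6), the HIV line in the synopsis, and primary objectives 3 and 5. They should ask about associations of HIV and comorbidity with outcomes already recorded among CAP patients: 28-day complications and hospitalization, 180-day survival, and pathogen. Clinical stability can be added for inpatients only, because it is recorded only at their day 3-5 and day 7-10 visits.

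Add one sentence saying that the risk of acquiring CAP is not estimated unless an external source of exposure prevalence is named. If such a claim is wanted, name that source and the population it represents.

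Any adjusted analysis should use covariates that precede the CAP episode, such as age, sex and smoking. Baseline vital signs should stay out of the main model: they are measured after onset, reflect severity, and may lie on the path from HIV or comorbidity to the outcome. Plan HIV comparisons on several pooled recruitment years.

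The cost is a wording amendment through Section 16.4, with ethics re-evaluation. No new data are needed for the within-CAP questions. The price is a narrower claim and a longer wait for the HIV results.
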